#### 10.3.1. Visual Analog Scales

Each VAS will be scored as an integer from 0 to 100. When appropriate, VASs will be administered as bipolar measures, meaning that the neutral point equals 50 (i.e., Drug Liking and Alertness/Drowsiness VAS). The neutral point will also be labeled with an anchor, such as

Version: 2.0, 17NOV2015 Page 56 of 99

"neither like nor dislike." Unipolar VASs (i.e., High, Good, Bad, and Any Effects VAS) are presented with anchors such as "not at all" (score = 0) to "extremely" (score = 100), where the neutral point equals 0. The use of a unipolar or bipolar scale is determined by the nature of the subjective effect being measured.

If precipitated withdrawal occurs after administration of CAM2038 q1w, subjects will be requested to complete a unipolar VAS assessment of opioid withdrawal severity.

Table 6 lists the subjective effects VAS question text and response anchors.

**Table 6** Visual Analog Scale Descriptions

Scale Interpretation	Description	Question Text	Response Anchors		
Balance	nce Drug Liking At this moment, my		0: Strong disliking 50: Neither like nor dislike 100: Strong liking		
Other effects	Any Drug Effects	At this moment, I feel any drug effects			
Positive	High	At this moment, I feel high			
Positive	Good Drug Effects	At this moment, I feel good drug effects	0: Not at all 100: Extremely		
Negative	Bad Drug Effects	At this moment, I feel bad drug effects			
Other Effects	Desire to use opioids	At this moment, I desire opioids	0: Definitely not 100: Definitely so		
Other Effects	Alertness/Drowsiness	At this moment, my mental state is	0: Very drowsy 50: Neither drowsy nor alert 100: Very alert		
Other Effects	Opioid Withdrawal Severity  I feel opioid withdrawal		0: Not at all 100: Extremely		

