#### 12.3.3.2. Secondary Efficacy Analyses

The secondary endpoints will include:

- Emax of High VAS
- Emax of Good Effects VAS
- Emax of Bad Effects VAS
- Emax of Sedated VAS
- Emax of Any Effects VAS
- Emax of Desire to use VAS

These variables will be analyzed using the similar methods discuss for the primary efficacy variable analyses.

COWS and OOWS scores will be summarized.

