9.0 EFFICACY ANALYSES

Many of the efficacy variables are visual analog scale (VAS) based. Each VAS will be scored as an integer from 0 to 100. When appropriate, VASs will be administered as bipolar measures, meaning

that the neutral point equals 50 (i.e., Drug Liking and Alertness/Drowsiness VAS). The neutral point will also be labeled with an anchor, such as “neither like nor dislike.” Unipolar VASs (i.e., High, Good, Bad, and Any Effects VAS) are presented with anchors such as “not at all” (score = 0) to “extremely” (score = 100), where the neutral point equals 0. The use of unipolar scale is determined by the nature of the subjective effect being measured. If precipitated withdrawal occurs after administration of CAM2038, patients will have a unipolar VAS assessment of opioid withdrawal severity.

The table lists the subjective effects VAS question text and response anchors.

Interpretation	Include Pre-dose	Description	Question Text	Response Anchors
Balance	No	Drug Liking	At this moment, my liking for this drug is	0: Strong disliking 50: Neither like nor dislike 100: Strong liking
Other effects	No	Any Drug Effects	At this moment, I feel any drug effects	0: Not at all 100: Extremely
Positive	Yes	High	At this moment, I feel high	
Positive	No	Good Drug Effects	At this moment, I feel good drug effects	
Negative	No	Bad Drug Effects	At this moment, I feel bad drug effects	
Other Effects	Yes	Desire to use opioids	At this moment, I desire opioids	0: Definitely not 100: Definitely so
Other Effects	Yes	Alertness/Drowsiness	At this moment, my mental state is	0: Very drowsy 50: Neither drowsy nor alert 100: Very alert

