9.1.1 DERIVATION OF E_{MAX} DRUG LIKING VAS

Four hydromorphone challenge sessions (3 consecutive days each with dose randomized) will be conducted on Days 1 to 3, Day 4 to 6, Days 8 to 10, and Days 11 to 13 after the first CAM2038 administration. Each Hydromorphone Challenge Session will consist of 3 doses of hydromorphone 10 mg/mL IM injections (doses of 0 mg [placebo], 6 mg and 18 mg) administered on 3 consecutive days in randomized order. The drug liking VAS will be rated by the subjects at predose and at 5, 10, 15, 30, 45,

60, 75, 90, 120, 150, 180, 210, 240, 270 and 300 minutes post-dose. The primary efficacy variable E_{\max} of drug liking VAS will be the maximum of the above post-dosing drug liking VAS scores.

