9.1.2 PRIMARY ANALYSIS

The primary analysis of the primary efficacy variable, E_{\max} of drug liking VAS, will be performed using the completer population. This variable will be analyzed via a mixed model including sequence (ABC, ACB, BAC, BCA, CAB, CBA), dosing (challenge dosing A=0 mg, B=6 mg, or C=18 mg), period (1, 2, or 3 to indicate first, second, or third day of each challenge session), session (challenge session 1, 2, 3, or 4), and dosing-by-session interaction as fixed effects, and subject as random effects. The maximum likelihood estimation will be used to estimate the parameters. Specifically, the following pseudo SAS codes will be used for the analysis:

```
proc mixed data=Efficacy_Data method=ml;
class SubjectID ChallengeDose Sequence Period Session;
model Emax=Sequence ChallengeDose Period Session ChallengeDose*Session;
random SubjectID / Subject= SubjectID;
LSMEANS ChallengeDose*Session/diff cl alpha=0.05;
Run;
```

The estimated treatment effects, differences in treatment effects (test dose – the reference dose of 0 mg), 95% confidence intervals of the differences will be presented. Blockade effects will be claimed if the upper bound of the treatment difference is ≤ 11 .

The same methodology will be used to analyze CAM2038 q1w 24 mg and 32 mg separately.

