9.2 SECONDARY EFFICACY OUTCOMES

In addition to the primary endpoint of change from baseline in E_{\max} of Drug Liking VAS, the following secondary endpoints will be calculated:

- High VAS E_{\max}
- Good Effects VAS E_{\max}
- Bad Effects VAS E_{\max}
- Sedated VAS E_{\max}
- Any Effects VAS E_{\max}
- Desire to use VAS E_{\max}

All these variables will be analyzed via the same methodology used to analyze the primary efficacy variable.

The follow secondary efficacy variables will be summarized by CAM2038 treatment group on the scheduled days that they are measured:

- Clinician-Rated Opioid Withdrawal Scale (COWS);
- Subjective Opioid Withdrawal Scale (SOWS);

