9.6 POWER AND SAMPLE SIZE JUSTIFICATION

A sample size of 24 subjects will provide 90% power for the CAM2038 32 mg to demonstrate no significant difference in the mean E_{\max} score of the Drug Liking VAS comparing to 0 mg hydromorphone at a two-sided 0.05 significance level with a non-significant difference cutoff at ≤ 11 points. In the sample size calculation it was assumed that the true difference was less than or equal to 1.5 and the standard deviation was 9.8.

Additional 24 subjects will be enrolled to CAM2038 24 mg group. This sample size will provide approximately 83% power for the CAM2038 24 mg to demonstrate no significant difference in the mean E_{\max} score of the Drug Liking VAS comparing to 0 mg hydromorphone at a two-sided 0.05 significance level with a non-significant difference cutoff at ≤ 11 points. In the sample size calculation it was assumed that the true difference was less than or equal to 2.5 and the standard deviation was 9.8.

The plan will be to enroll a sufficient number of subjects to ensure that approximately 48 subjects complete the study (24 subjects per treatment group) by over-enrollment as needed.

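### Desire to Use is judged by the Drug Liking rule, which sees only increases: if unblocked hydromorphone lowers desire, this secondary scale would read as blockade

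*SAP*

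**What the plan says.** SAP 9.2 lists Emax of the Desire to Use VAS among six secondary endpoints and continues: "All these variables will be analyzed via the same methodology used to analyze the primary efficacy variable". Protocol 12.3.3.2 is looser ("These variables will be analyzed using the similar methods discuss for the primary efficacy variable analyses") but makes no exception for any scale.

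The primary methodology has three parts.

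- SAP 9.1.1: Emax "of drug liking VAS will be the maximum of the above post-dosing drug liking VAS scores". The ratings run from 5 to 300 minutes, and the pre-dose rating is not used.
- SAP 9.1.2: the contrast is "differences in treatment effects (test dose – the reference dose of 0 mg").
- SAP 9.1.2: "Blockade effects will be claimed if the upper bound of the treatment difference is" at most 11. There is no lower bound.

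Desire to Use asks for agreement with "At this moment, I desire opioids" (Protocol 10.3.1, Table 6), anchored "0: Definitely not 100: Definitely so" (SAP 9.0), so a fall in desire is a negative difference. Neither document says which way unblocked hydromorphone should move this scale, and neither gives it a margin of its own. Protocol Table 4 collects every scale before each challenge dose as well as after it.

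**The concern.** Drug Liking asks about the drug just given. Desire to Use asks about a state that can be present before the injection, and inclusion criterion 3 requires physical dependence on opioids. A failure of blockade could therefore show as a rise or as a fall. The plan's rule can detect only the rise. A fall makes the difference negative, moves the upper bound further below 11, and is labelled as blockade.

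A maximum adds to this. It picks out the highest rating of the session, so a fall that starts after the first ratings, or wears off before the last ones, is partly hidden in the reported difference.

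At stake is one secondary scale. The secondary objective is the degree of blockade on the secondary measures, and Protocol 10.5 says the additional scales are collected to back up the primary result. A scale that can read as blocked both under full blockade and under failed blockade with a fall in desire does not provide that backing.

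**Working it through.** **Inputs from the documents.** 24 subjects per group, SD 9.8, margin 11, and a "two-sided 0.05 significance level with a non-significant difference cutoff at" 11 points (SAP 9.6). These were set for Drug Liking; no SD is given for Desire to Use.

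**1. Reproduce the stated power.** Let d be the true difference, test dose minus 0 mg. A two-sample form gives SE = 9.8 × √(2/24) = 2.829. The probability that the upper bound is at most 11 is the upper tail of a noncentral t on 46 df with noncentrality (11 − d)/SE, beyond the 0.975 quantile of the central t.

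- d = 1.5: 9.5/2.829 = 3.36, power 90.8% (stated 90%).
- d = 2.5: 8.5/2.829 = 3.00, power 83.7% (stated about 83%).

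A paired form with SE = 9.8/√24 gives 99.5% and 98.2%, which does not match, so the two-sample form is used below.

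**2. The same rule at other true differences.**

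| True difference | (11 − d)/SE | Probability the rule reads blockade |
|---|---|---|
| +20 | -3.18 | below 0.001% |
| +11 | 0 | 2.5% |
| 0 | 3.89 | 96.8% |
| -5 | 5.66 | 99.98% |
| -10 | 7.42 | above 99.99% |
| -20 | 10.96 | above 99.99% |

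**3. Larger assumed SDs** (normal approximation, because the SD for this scale is unknown).

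| SD | d = 0 | d = -10 | d = -20 |
|---|---|---|---|
| 15 | 71.9% | 99.8% | above 99.9% |
| 20 | 47.8% | 95.3% | above 99.9% |
| 25 | 33.2% | 82.9% | 99.0% |
| 30 | 24.5% | 67.9% | 94.7% |

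At every SD checked, a fall passes more easily than true blockade (difference 0).

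**4. How far the maximum hides a fall.** This is a simulation at the 15 planned post-dose times, on assumptions that are not in the documents: pre-dose level 50 (SD 10), rating noise SD 3 to 5, and a sustained fall of 25 points from a given time.

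| Fall present from | Difference in maximum | Difference in minimum |
|---|---|---|
| 30 min | -2.7 to -4.5 | about -24 to -25 |
| 10 min | -5.2 to -8.7 | about -25 |
| 5 min | about -25 | about -25 |

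All these Emax differences lie below 11. Onset changes the size of the Emax difference, not its sign.

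**5. Gradual onset and offset.** Assumptions: 24 subjects, pre-dose level 50 (SD 20), noise SD 5, no blockade, peak fall of 20 to 40 points, two onset and offset shapes, paired t interval. Emax differences averaged -8.5 to -18.3, and the planned rule read blockade in 100% of runs. A check on the post-dose minimum (lower bound at least -11) read blockade in 0% of those runs and in 100% of runs with no drug effect. With a peak rise of 30 points, the planned rule read blockade in 0% of runs, as it should.

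**6. Low pre-dose desire.** With a pre-dose level of 10 and the same size of fall cut off at zero, the minimum differs by only about -5 to -7. Where there is little room to fall, the minimum shows little too.

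**The case against.** The main objection is that the direction is not in the documents. No section says that hydromorphone lowers desire in these subjects, or gives an onset time after an IM dose. If desire rises, the rule works. That stands, and it makes the point conditional.

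A reader might go further and infer that Emax will simply repeat the pre-dose level, so that the difference is near zero. The documents do not support that. It follows from assuming that the fall begins at about 30 minutes; if it is present from 5 minutes, Emax takes the full fall.

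The modelled sessions all follow CAM2038, and Protocol 9.4 describes buprenorphine levels even below 2 ng/mL as effective in suppressing withdrawal. Pre-dose desire may therefore already be low, leaving little room to fall. This also stands, and it limits what any measure of decrease can show.

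SAP 9.1.2 requires estimates, differences and 95% intervals, so a clearly negative difference would be visible to a careful reader. That reduces the harm but does not change the label that the rule attaches.

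It can also be said that the claim sentence is written under the primary analysis and reaches Desire to Use only through the reference to the same methodology. That is a fair limit, although extending it is the natural reading of SAP 9.2.

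Finally, a reader might infer that the trial's blockade claim is weakened. It is not: that claim rests on Drug Liking, and the testing order in SAP 9.4 names no secondary scale.

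**Conclusion.** The point holds as a conditional one. The rule carried over to Desire to Use cannot register a decrease, so if unblocked hydromorphone lowers desire, failed blockade reads as blockade. With the Drug Liking planning inputs the probability of that reading is above 99.99% at a true difference of -10 or lower; at an SD of 30 it is still 67.9% at -10 and 94.7% at -20.

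The direction and size of any fall are assumptions. For an assumed 25-point fall the Emax difference is about -3 to -25 points depending on onset, and the fall itself may be small if desire is already low under CAM2038. The documents do not support saying that the endpoint will mislead, only that it cannot tell the two cases apart if desire falls. The effect is confined to one secondary scale, so this is a low-cost improvement rather than a defect in the primary analysis.

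**What to change.** In SAP 9.2:

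1. Keep Emax of Desire to Use as a reported summary, and state that no blockade claim will be made for this scale from the upper-bound rule of 11.
2. Add the change from that day's pre-dose rating to the post-dose minimum and to the post-dose maximum. Compare each with 0 mg in the same mixed model, with two-sided 95% confidence intervals.
3. Report the same contrasts from the Qualification session (Days -3 to -1), leaving out the session terms because there is only one session. It precedes CAM2038, so it shows the direction and size of the unblocked effect.

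The cost is SAP text and one or two extra derived variables. Protocol Table 4 already collects all the ratings. The downside is one fewer secondary scale on which blockade can be formally claimed.

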# 8.3. Qualification Criteria

In addition to the inclusion and exclusion criteria, subjects must meet each one of the following criteria in order to be eligible for participation in the Treatment Phase:

- Maximum effect (Emax) in response to IM hydromorphone 6 mg greater than that of placebo on Drug Liking bipolar VAS (response to hydromorphone 6 mg should be greater than 55 mm in the VAS and a difference of at least 15 mm between placebo and 6 mg) and acceptable overall responses to hydromorphone and placebo on the subjective measures, as judged by the Investigator or designee.
- Emax in response to IM hydromorphone 18 mg greater than that of placebo on Drug Liking bipolar VAS (greater than 60 mm and a difference of at least 20 mm between placebo and 18 mg) and Emax score of at least 20 points, and acceptable overall responses to hydromorphone and placebo on the subjective measures, as judged by the Investigator or designee.
- Acceptable placebo response based on Drug Liking bipolar VAS (score between 40 and 60 mm, inclusive).
- Subject is able to tolerate IM hydromorphone 6 mg and 18 mg, as judged by the Investigator, including ability to complete most pharmacodynamic assessments administered within 5 hours post-dose.
- General behavior suggests that the subject could successfully complete the study, as judged by the research site staff.

Version: 2.0, 17NOV2015 Page 46 of 99

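### As SAP 9.2 naturally reads, Bad Effects is put to the Drug Liking blockade rule although no unblocked Bad Effects response is required, so a pass on that scale need not mean blockade

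*SAP*

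**What the plan says.** SAP 9.2 names six secondary Emax variables, Bad Effects among them, and states: "All these variables will be analyzed via the same methodology used to analyze the primary efficacy variable". SAP 9.1.2 sets out that methodology. It fits a mixed model separately in each CAM2038 group, gives dose-by-session least-squares means, and forms test-minus-0 mg differences with 95% confidence intervals. It then adds one decision rule: "Blockade effects will be claimed if the upper bound of the treatment difference is" no more than 11. The model covers challenge sessions 1 to 4, so the Qualification session lies outside it. Neither document gives Bad Effects its own margin or exempts it. The protocol's wording in 12.3.3.2 is softer: "These variables will be analyzed using the similar methods discuss for the primary efficacy variable analyses".

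Protocol 8.3 sets numeric entry requirements for Drug Liking only. For the lower dose the requirement is "response to hydromorphone 6 mg should be greater than 55 mm in the VAS and a difference of at least 15 mm between placebo and" that dose. For 18 mg the score must exceed 60 and be at least 20 mm above placebo. For the remaining scales the investigator or designee need only judge the responses acceptable overall.

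Bad Effects is a unipolar 0 to 100 item in Protocol Table 6 ("At this moment, I feel bad drug effects"). Protocol Table 4 has it collected on Days -3 to -1 as well as in the treatment sessions. SAP Appendix A plans Tables 14.2.4.1a to 14.2.4.2b for this scale. No listed table or figure is titled as a Qualification-session comparison of it.

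**The concern.** A rule of the form 'not more than 11 above placebo' works like a non-inferiority test and depends on assay sensitivity. It is evidence of blockade only if the same dose, given without CAM2038, would have moved the scale by more than 11. For Drug Liking the entry criteria supply that evidence subject by subject. For Bad Effects nothing does. A subject who reports no bad effects at any dose can qualify, and then pulls the group difference towards a pass whether or not CAM2038 blocks anything.

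There is no placebo-depot group. Protocol 7.2 gives the Qualification session the task of showing what happens without CAM2038, but the planned analysis of Bad Effects does not use it.

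What is at stake is the first secondary objective, which assesses blockade through the secondary measures. A pass on Bad Effects could be tabulated as supporting blockade when it shows only that the sample reported few bad effects from hydromorphone.

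**Working it through.** **Inputs.** From SAP 9.6: 24 subjects per group, two-sided 0.05, margin 11, SD 9.8, true differences 1.5 (32 mg) and 2.5 (24 mg), all for Drug Liking. From Protocol 8.3: minimum Drug Liking differences of 15 and 20 mm. Assumed, because the documents are silent: the Bad Effects SD (9.8, 15 or 20) and the unblocked Bad Effects difference *d*.

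**Formula.** SE = SD × √(2/24). The rule is met with probability P = 1 − F(t*; 46, (11 − *d*)/SE). Here F is the noncentral t distribution function with 46 degrees of freedom and t* is its central 97.5% point, 2.013.

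**Reproducing the plan's power.** SE = 9.8 × √(2/24) = 2.83.
- *d* = 1.5: noncentrality 9.5/2.83 = 3.36, P = 90.8% (plan: 90%).
- *d* = 2.5: noncentrality 8.5/2.83 = 3.00, P = 83.7% (plan: about 83%).

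The formula recovers both figures. Taking 9.8 as the SD of a within-subject difference does not: it gives 99.5% and 98.2%.

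**Applying it to Bad Effects.** Suppose CAM2038 changes nothing, so the treatment-session difference equals the unblocked difference *d*. SE is 2.83, 4.33 and 5.77 for SD 9.8, 15 and 20. The chance of meeting the rule, for one dose in one session, is:

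| Unblocked difference *d* | SD 9.8 | SD 15 | SD 20 |
|---|---|---|---|
| 0 | 96.8% | 70.1% | 46.2% |
| 2.5 | 83.7% | 48.5% | 30.2% |
| 5 | 54.6% | 27.3% | 17.3% |
| 8 | 17.8% | 10.0% | 7.3% |
| 11 | 2.5% | 2.5% | 2.5% |
| 15 | 0.04% | 0.2% | 0.4% |

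The pass rate falls as the SD grows because the interval widens, not because the rule becomes better at detecting blockade. If blockade brought a true unblocked difference of 5 down to 0, the pass rate would be 97% against 55% with no blockade at SD 9.8, and 46% against 17% at SD 20.

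**Contrast with Drug Liking.** At SD 9.8, if the required 15 mm difference persisted unblocked, the rule would be met 0.04% of the time, and at 20 mm practically never. The same rule is therefore protected on Drug Liking and unprotected on Bad Effects.

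**The case against.** **The rule may not carry over.** The claim sentence stands under the primary analysis, and SAP 9.6 attaches the margin to Drug Liking ("at a two-sided 0.05 significance level with a non-significant difference cutoff at" 11 points). The protocol says only that the methods are similar. One could carry over the model, estimates and intervals and leave the rule behind. That reading is possible, and a reader who takes the rule's use on Bad Effects as expressly stated goes too far. But SAP 9.2 makes no exception, and the rule is the only decision criterion in the methodology it invokes, so carry-over is the natural reading.

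**Subjects may well have bad effects.** A reader might infer that people who like and tolerate hydromorphone report none. The documents do not show that. Liking and Bad Effects are separate scales, each Emax is a single maximum over five hours, and toleration is an investigator's judgment. If the unblocked difference is clearly above 11, the rule works. This objection stands as a limit: the plan does not establish the unblocked difference either way.

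**The high figure is conditional.** The 97% needs both a zero difference and the Drug Liking SD, so it is not an expected error rate. The SAP does not say whether a claim needs every session to pass. If it did, a simulation with independent residuals of SD 9.8 gives about 90% for all four sessions at 6 mg when the difference is 0, but about 10% when it is 5.

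**Other scales share the gap.** High, Good Effects and Any Effects have no numeric minimum either. That is true. Bad Effects is the clearest case because entry requires liking and tolerating both doses, which gives no assurance of a negative response.

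**Conclusion.** The point holds in limited form. As SAP 9.2 naturally reads, a blockade result on Bad Effects can arise with nothing blocked, and the plan has no step that would reveal it. For one dose in one session, the chance of such a result with no blockade runs from 46% to 97% if the unblocked difference is 0, and from 17% to 55% if it is 5, across SDs of 20 down to 9.8. These figures rest on assumed means and SDs and on the two-sample t approximation that reproduces the plan's power.

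A reader might go on to infer that the trial's main blockade claim is unsafe. It is not affected: Drug Liking has its own entry minimums, and the four ordered comparisons in SAP 9.4 do not name a secondary scale. The consequence is confined to a secondary objective, but it is worth correcting because the correction is so small.

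**What to change.** In SAP 9.2, state that the 11-point blockade rule does not apply to Bad Effects Emax. Report its 6 mg and 18 mg minus 0 mg differences, with 95% confidence intervals by session, as tolerability results. Show the corresponding Qualification-session difference (Days -3 to -1) in the same tables, so that the reader can see how much response there was without CAM2038.

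This takes one or two sentences and one extra estimate from data already collected. The downside is that one secondary scale no longer counts as supporting blockade.
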